5. STATISTICAL HYPOTHESES FOR STUDY OBJECTIVES

5.1. Primary Hypotheses

All primary hypotheses must be met in order to satisfy the primary objective of this study.

1. The Test lens will be non-inferior to the Control lens with respect to Distance Monocular logMAR Visual Acuity at the two-week follow-up evaluation under both lighting conditions (Bright illumination low contrast and dim illumination high contrast). A non-inferiority margin of 0.05 logMAR will be used.

2. The Test lens will be non-inferior to the Control lens with respect to the percentage of eyes with Grade 3 or higher Slit Lamp Findings (Biomicroscopy) across all follow-up visits (scheduled and unscheduled). A non-inferiority odds ratio margin of 2 will be used.
3. The proportion of eyes with acceptable fit will be greater than 90% across all visits (scheduled and unscheduled) for all subjects wearing the Test lens.
4. The Test lens will be non-inferior to the Control lens with respect to CLUE Overall Comfort at the two-week follow-up evaluation. A non-inferiority margin of -5 points will be used.
5. The Test lens will be non-inferior to the Control lens with respect to Vision satisfaction in bright lighting at the two-week follow-up evaluation. A non-inferiority cumulative odds ratio margin of 0.67 will be used.

5.2. Secondary Hypotheses

1. The Test lens will be non-inferior to the Control lens with respect to CLUE Overall quality of vision at the two-week follow-up evaluation. A non-inferiority margin of -5 points will be used.
2. The Test lens will be non-inferior to the Control with respect to CLUE Handling at the two-week follow-up evaluation. A non-inferiority margin of -5 points will be used.
3. The Test lens will be non-inferior the Control lens with respect to Overall quality of vision indoors at the 2-week follow-up evaluation. A non-inferiority cumulative odds ratio margin of 0.67 will be used.

5.3. Other Hypotheses

1. The Test lens will be superior to the Control lens in all 9 of the following lens preference items at the two-week follow-up evaluation of the second wearing period.
 - a) Overall lens preference
 - b) Overall comfort
 - c) Overall vision
 - d) Overall reduction of glare
 - e) Overall preference indoors
 - f) Overall preference outdoors
 - g) Overall preference while driving during the day
 - h) Overall preference while driving at night
 - i) Overall preference while using computer screens & digital devices
2. The Test lens will be superior to the Control lens in at least 2 of the following 4 indoor performance measures at the two-week follow-up evaluation.
 - a) Reduction in squinting while using computer screens or digital devices

- b) Reduction in glare from the computer screen or digital devices
- c) Reduction in glare caused by bright indoor lights
- d) Reduction in glare caused by bright light coming through the window

3. The Test lens will be non-inferior to the Control lens with respect to both of the following driving performance metrics at the two-week follow-up evaluation. A cumulative odds ratio margin of 0.67 will be used.

- a) Reduction in glare while driving during the day
- b) Reduction in glare while driving during the night

4. The Test lens will be superior to the Control lens in at least 2 of the following 4 outdoor performance measures at the two-week follow-up evaluation.

- a) Ability to see comfortably in bright sunlight
- b) Reduction in glare in bright sunlight
- c) Reduction in squinting in bright sunlight
- d) Reduction in eye strain in bright sunlight

5. At the 2-week follow-up evaluation, the difference in the area under the contrast sensitivity function curve (measured by the quick Contrast Sensitivity Function (qCSF) method) between the Test lens and the Control lens is more than -0.3 log unit.

6. ANALYSIS SETS

6.1. All Enrolled

The All Enrolled population will include all participants who sign an informed consent.

6.2. Intent-to-Treat (ITT)

Intent-to-treat will include all the subjects who were randomized to study treatment. Subject will be analyzed as per randomized treatment (Planned Arm).

6.3. Safety Population

This analysis population will include all subjects who are randomized and administered any test article. Safety analyses will be based on the safety population.

6.4. Per-Protocol (PP)

Per Protocol Analysis set will be the primary analysis population. It will include all subjects who have successfully completed all visits and did not substantially deviate from the protocol as determined by the trial cohort review committee prior to database hard lock. Justification of excluding subjects with protocol deviations in the per-protocol population set will be documented in a memo to file.

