8.2. Withdrawal/Discontinuation from the Study

A subject will be withdrawn from the study for any of the following reasons:

- Subject death during the study period
- Subject withdrawal of consent
- Subject not compliant to protocol (e.g. Subject more than 2 days out of visit window).
- Subject lost to follow-up
- Subject no longer meets eligibility criteria (e.g. the subject becomes pregnant)
- Subject develops significant or serious adverse events causing discontinuation of study lens wear (subjects missing more than 2 days of missed lens wear within a period 1 of week should be discontinued)
- Subjects who have experienced a Corneal Infiltrative Event (CIE)
- Investigator's clinical judgment regarding the subject safety reasons (that it is in the best interest of the subject to stop treatment)
- Subject missed any scheduled study visits
- Subject not compliant with study lens wear schedule
- Subject not successfully dispensed due to lack of efficacy and safety including poor vision, poor comfort or unacceptable fit

For discontinued subjects, the Investigator will:

- Complete the current visit (scheduled or unscheduled)
- Complete the Final Evaluation, indicating the reason that the subject was discontinued from the study
- Record the spherocylindrical refraction with best corrected distance visual acuity
- Collect used test article(s) (worn or brought to the visit) from the subject and discard them, unless otherwise stated in Section 7.2.
- Collect all unused test article(s) from the subject

Investigator will discuss with sponsor before enrolling any additional subjects if a subject discontinues from the study prematurely.

In cases where a subject is lost to follow-up, every possible effort must be made to contact the subject and determine the reason for discontinuation/withdrawal. The measures taken to

follow up must be documented including two written attempts and a certified letter (or equivalent) as the final attempt.

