8.6. Handling of Missing Data and Drop-outs

Missing or spurious values will not be imputed. The count of missing values will be included in the summary tables and listings.

Subject dropout is expected to be one of the main reasons of missing data in this clinical trial. Past clinical trials don't provide the evidence that subject dropout is systematic or not-atrandom. To evaluate the impact of missing data, sensitivity analysis will be conducted using multiple imputation methods if the proportion of subject dropout is greater than the 15%. The SAS/STAT procedures PROC MI and PROC MIANALYZE will be utilized with a parametric regression method used to make at least 10 imputations.

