10.3. Demographics and Baseline Characteristics

Demographic characteristics will be summarized by Per-Protocol, safety, all enrolled and by lens sequence population using descriptive statistics for continuous variables, and numbers and percentages of subjects for categorical variables. Demographic information will include age, gender, race and ethnicity and iris category.

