We assume the random subject eye effects are i.i.d as $\alpha_{j(m(l))} \sim N(0, \sigma_{eye}^2)$ for eye nested within subject within clinical site, the random effect for subject are i.i.d as $\delta_{m(l)} \sim N(0, \sigma_{subject}^2)$ for subject nested within clinical site and the random clinical site effects are i.i.d as $\gamma_m \sim N(0, \sigma_{site}^2)$ for i=1, 2 (eye) , j=1, 2, 3 (period) k=1, 2 (Sequence) l=1, ...6 (Site) m=1, ...n_l(subject/site).

For the β coefficients, independent non-informative priors $N(0, 10000)$ will be used. For the variance of random effects of $\sigma_{eye}^2, \sigma_{subject}^2$ and σ_{site}^2 , independent non-informative conjugate priors inverse-gamma (0.001, 0.001) will be used. The Metropolis-Hastings algorithm as implemented in the SAS/STAT 14.2 PROC MCMC procedure will be used to estimate posterior distributions of the unknown parameters. Inferences will be made based on the posterior credible interval for the relevant parameters.

Hypothesis Testing

With respect to acceptable lens fit the null and alternative hypothesis for superiority is as follows:

$$\begin{aligned} H_0 &= p \leq 0.90 \\ H_1 &= p > 0.90 \end{aligned}$$

Where, p represents the proportion of subject eyes that achieve acceptable fit for the Test lens.

Where p is calculated as:

$$p = \frac{\exp(\mu)}{1 + \exp(\mu)}$$

$$\text{And } \mu = \beta_0 + \beta_1 + \frac{\beta_3}{3} + \frac{\beta_4}{3} + \frac{\beta_5}{2} + \frac{\beta_6}{2}$$

Success for acceptable fit will be declared if the lower bound of the 2-sided 95% credible interval of the proportion is greater than 0.90; i.e. $P(p > 0.90) \geq .975$.

If the full planned model fails to converge, reduced versions may be considered.

Primary safety analysis:

Slit Lamp Findings

Grade 3 or higher slit lamp findings will be analyzed using a Bayesian Logistic regression random-effects model to compare the Test and Control lenses. The regression model will include baseline slit lamp findings, lens type, period, sequence of lens wear and first order carryover effect. Site and subject will be included in the model as random effects.

Let $y_{ijklmn}=1$ if a Grade 3 or higher SLF is observed and $y_{ijklmn}=0$ otherwise for the n^{th} subject, from the m^{th} site, assigned to the i^{th} study lens for the j^{th} eye in the k^{th} period using the l^{th} sequence.

$$y_{ijklmn} \sim \text{Binary}(p_{ijklmn})$$

$$p_{ijklmn} = \frac{\exp(\mu_{ijklmn})}{1 + \exp(\mu_{ijklmn})}$$

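### The efficacy non-inferiority tests lead on per-protocol completers with no ITT analysis beside them, the only missing-data sensitivity does not run at the planned dropout, and the SAP conflicts on the set for slit lamp and fit

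*SAP*

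**What the plan says.** - **Lead set.** SAP 6.4: "Per Protocol Analysis set will be the primary analysis population". On membership: "It will include all subjects who have successfully completed all visits and did not substantially deviate from the protocol". SAP 10.2 also excludes anyone with a deviation that could affect a primary endpoint.
- **ITT.** SAP 6.2: "Intent-to-treat will include all the subjects who were randomized to study treatment". Protocol 14.3 defines the set too. SAP 11.1 and 11.2 never use it, and the demographic tables in SAP 10.3 omit it: "Demographic characteristics will be summarized by Per-Protocol, safety, all enrolled and by lens sequence population".
- **Missing data.** SAP 8.6 imputes nothing in the main analysis. It adds multiple imputation only "if the proportion of subject dropout is greater than the 15" per cent, and does not say on which set.
- **Withdrawal tied to outcome.** One reason in Protocol 8.2 is: "Subject not successfully dispensed due to lack of efficacy and safety including poor vision, poor comfort or unacceptable fit". Missed visits and non-compliance with lens wear are others.
- **Safety set.** SAP 6.3: "Safety analyses will be based on the safety population". SAP 11.1 places fit acceptance and slit lamp findings under primary safety headings ("Grade 3 or higher slit lamp findings will be analyzed using a Bayesian Logistic regression random-effects model to compare the Test and Control lenses"), but names no set for either.

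**The concern.** Six efficacy tests are involved: logMAR acuity, CLUE comfort, bright-light satisfaction, CLUE vision, CLUE handling and vision indoors. As planned, each describes subjects who got through all three periods on both lenses. Anyone who leaves contributes nothing, even where one or two follow-ups are complete. Per-protocol as the lead set is defensible for non-inferiority. The weakness is that nothing stands beside it: no all-randomised fit, and no sensitivity analysis at the loss the plan expects. If withdrawal depends on how a lens performs, the reported comparison is of a selected group and no planned table would show it. Complete masking to the Test lens is not possible (Protocol 5.2), so lens-dependent withdrawal cannot be ruled out.

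The two safety endpoints have a different problem. If the general statement in SAP 6.4 governed them, subjects removed from the study because of the event would also be removed from the test that counts the event.

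**Working it through.** **1. Planned loss (SAP 8.4 and Table 2).** 120 enrolled, 105 to complete: (120 - 105)/120 = 15/120 = 12.5%. SAP Table 2 plans 120 enrolled, 114 randomised and 108 completed: 12/120 = 10.0% of enrolled, or 6/114 = 5.3% of randomised.

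**2. Trigger (SAP 8.6).** 18/120 = 15.0%, which is not above 15%; 19/120 = 15.8%. So 19 dropouts are needed, against 15 or 12 planned.

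**3. Historical loss, enrolled to per-protocol completion (SAP Table 5).**

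| Enrolled | Completed PP | Loss |
|---|---|---|
| 135 | 132 | 2.2% |
| 133 | 121 | 9.0% |
| 92 | 78 | 15.2% |
| 54 | 48 | 11.1% |
| 56 | 41 | 26.8% |
| 470 | 420 | 50/470 = 10.6% |

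Two of five studies exceed 15%; the pooled rate does not. This measure may include exclusions for deviations, so it is only a guide to dropout as SAP 8.6 means it.

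**4. How far CLUE comfort could move.** The documents give no result for leavers, so their mean Test-minus-Control difference, δ, is an assumption, and I solve for the value that would change the conclusion.

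- Standard error: generalised least squares with the 3×3 comfort covariance in SAP 8.4, lens as the only fixed effect (the SAP's sizing model) and equal sequences. Var(β1) is the lens element of (Σₛ nₛ Xₛ′V⁻¹Xₛ)⁻¹, with lens coded 1,0,0 for Test/Control/Control and 0,1,1 for Control/Test/Test. SE = 1.95 at n = 105 and 1.83 at n = 120.
- Check on this SE: at n = 30 it is 3.65. With a distance of 10 points to the margin (+5 effect, -5 margin), power is about 85–86% at one-sided 5%, close to the stated 87%. Under the stated decision rule (one-sided 2.5%) it is about 75–77%, which is a separate matter.
- Per-protocol lower bound for an observed difference D: D - 1.96 × 1.952 = D - 3.83.
- All-randomised difference if leavers' results were known: (1 - w)D + wδ, where w is the fraction leaving. Its lower bound subtracts 1.96 × 1.826 = 3.58, so it reaches -5 when the difference is -1.42. Hence δ = (-1.42 - (1 - w)D)/w.

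| Completers' difference D | PP lower bound | δ, 15 leavers (w = 0.125) | δ, 18 leavers (w = 0.15) |
|---|---|---|---|
| 0 | -3.8 (pass) | -11.4 | -9.5 |
| -1 | -4.8 (pass) | -4.4 | -3.8 |
| +5 (assumed in SAP 8.4) | +1.2 (pass) | -46.4 | -37.8 |

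For example, D = -1 and w = 0.125 gives (-1.42 + 0.875)/0.125 = -4.4. Eighteen is the largest loss that still does not start the imputation.

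**5. Slit lamp and fit under each set.** The Visit 1 to 3 procedures (Protocol 7.2) discontinue a subject with unacceptable fit. Visits 2 and 3 terminate a subject with a Grade 3 or higher finding once it has resolved. Neither subject can complete all visits, so neither can be per-protocol. Removing every subject discontinued for fit pushes per-protocol fit towards 100% by construction. As a subject-level simplification, 6 such exits among 120 give 114/120 = 95.0% with an exact lower 95% limit of 0.894, already below 0.90. Fifteen give 105/120 = 87.5% and eighteen give 102/120 = 85.0%, still without a sensitivity run. Under the safety population these subjects stay in.

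**The case against.** Five points can be made for the plan.

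- **Safety endpoints.** A reader might infer that every non-inferiority test is confined to completers. The documents do not support that. SAP 6.3 puts safety analyses on the safety population, and slit lamp findings and fit are labelled primary safety. What stands is that 6.4 makes no exception and 11.1 names no set, so the SAP conflicts with itself on these two.
- **Direction.** A reader might infer that dropping leavers favours the Test lens. That is not shown. Historical comfort favours Test (66.46 against 61.19). If Control is the worse-tolerated lens, losing its leavers works against Test. This objection stands in full.
- **What ITT can recover.** The quoted withdrawal reason concerns failure at dispensing. A subject failing at Visit 1 has no follow-up; a Control/Test/Test subject failing at Visit 2 has only Control data; and unscheduled visits are excluded from analysis (SAP 8.2). An all-available-periods fit recovers only subjects with completed follow-ups. This also stands, and is why the imputation is needed as well.
- **The sensitivity can run.** It can, at 19 of 120, and two historical studies lost more than 15% on a related measure. A reader might infer that it never runs; the documents show only that it does not run at the planned rate.
- **Stage.** This is a Phase 2b initial evaluation ahead of a design validation study. Requiring ITT to reach the same conclusion would change the success rule, and nothing in the documents calls for that. A supportive analysis leaves the rule alone.

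**Conclusion.** The concern holds for the six efficacy tests: per-protocol is the lead set, ITT is defined and unused, and the sensitivity needs 19 of 120 dropouts against 15 or 12 planned. At the expected loss, selection through outcome-related withdrawal would go unseen.

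Its consequence is conditional. For CLUE comfort, with 15 leavers, a per-protocol pass would be reversed if leavers averaged about -11 points when completers show no difference, or about -4 when completers show -1. At the assumed +5 it would take about -46, so the result would be robust. These figures rest on the SAP's covariance, equal sequences and an assumed effect in leavers; they are thresholds, not estimates of bias. The gap matters if the lenses are close or Test is worse tolerated.

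The conflict between SAP 6.3 and 6.4 over slit lamp and fit is a separate defect. It needs resolving because the per-protocol reading would take events out of the tests that count them.

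**What to change.** 1. **SAP 6.2 and 11.** Keep per-protocol as lead for efficacy. Also fit each primary and secondary efficacy model to all randomised subjects with at least one follow-up observation, using all available periods. Report it beside per-protocol as supportive, and discuss any disagreement. The multivariate normal models in 11.1 are written for a full three-period vector, so state that an incomplete subject contributes the observed periods.
2. **SAP 8.6.** Delete the 15% trigger and run the multiple imputation on the ITT set whatever the dropout, so that subjects without Test-lens follow-up are covered. Regression imputation borrows from subjects with data, so report the reasons for withdrawal by lens alongside it.
3. **SAP 6.3, 6.4 and 11.1.** State that slit lamp findings and fit are analysed on the safety population.

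The cost is one further run of each efficacy model, an imputation run, and possibly a less favourable supportive result. Sample size, visits and the success rule for the efficacy tests are unchanged.

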		██████████ will be emphasized using the 1.0 increment scale for internal purposes only.	
1.11	Iris Color	The investigator will record the subject's iris color based on the scale provided.	Appendix E
1.12	Subjective Refraction	The investigator will complete a subjective refraction (sphere and cylinder) and record the resultant distance visual acuity OD, OS, and OU to the nearest letter. Best corrected distance visual acuity (BVA) must be 20/25+3 or better in each eye.	██████████
1.13	Eligibility after Baseline	All responses to Inclusion Criteria questions must be answered "yes" and all responses to Exclusion Criteria questions must be answered "no" for the subject to be considered eligible.	
1.14	Eye Rinse	The study coordinator, investigator, or technician will rinse the subject's eyes thoroughly with saline.	

Visit 1: Treatment 1 Lens Fitting			
Step	Procedure	Details	
1.15	Lens Selection	Assign the study lens based on the randomization scheme. Select the contact lens power based on subjective refraction.	
1.16	Lens Insertion	The Investigator or the subject inserts the study lenses. Record the time of lens insertion. Check for lens damage under the slit lamp before proceeding with lens settling. Replace damaged lenses if applicable.	
1.17	Lens Settling	Allow the study lenses to settle for a minimum of 5 minutes.	
1.18	Spherical Over Refraction and Modification	Perform a spherical over-refraction OD and OS. Optimize the lens power to achieve an over-refraction of ± 0.00 D OD and OS.	

Visit 1: Treatment 1 Lens Fitting			
Step	Procedure	Details	
		Ensure that any new lenses are not damaged. One modification attempt will be allowed.	
1.19	Time Interval	Please wait for at least 10 minutes from final lens insertion to continue.	
1.20	Subject Reported Ocular Symptoms	Subjects will respond to a verbal open-ended symptoms questionnaire.	
1.21	Visual Acuity	Record the distance Snellen visual acuity with the contact lenses (OD, OS, and OU) to the nearest letter. Smaller lines must be shown until the subject incorrectly identifies at least 50% of the letters.	
1.22	Subjective Lens Fit Assessment	
Subjective Assessment of the Lens Fit. If the fit is graded as unacceptable based on the criteria below, then the subject is discontinued from the study and will not be replaced.
 
 1. Limbal exposure in any gaze 2. Edge lift 3. Insufficient and/or excessive movement in all three movement categories 	

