2.5.	Follow-Up Questionnaire	Subjects will respond to the following questionnaires: 1. CLUE Follow-up 2. GSI Product Performance	
2.6.	Visual Acuity	Record the distance Snellen visual acuity with the contact lenses (OD, OS, and OU) to the nearest letter. Subjects must read the smallest line until at least 50% of the letters are read incorrectly.	
2.7.	Quick Contrast Sensitivity	████████ only. Perform the 4 m contrast sensitivity test once OD and OS using the 25-item methodology while wearing the study lenses.	
2.8.	logMAR (ETDRS) Visual Acuity	Perform 4 m distance ETDRS LogMAR visual acuity test OD and OS under the following conditions: 1. Bright room illumination / low contrast charts a. Room illumination >400 lux b. Chart luminance 120-200 cd/m ² c. One low contrast chart per eye. 1) OD: chart LC-1 2) OS: chart LC-2 2. Low room illumination / high contrast charts a. Room illumination <2.5 lux b. Chart luminance 2.0-5.0 cd/m ² c. One high contrast chart per eye. 1) OD: chart HC-1 2) OS: chart HC-2	████████ ████████
2.9.	Subjective Lens Fit Assessment	Subjective Assessment of the Lens Fit. If the fit is graded as unacceptable based on the criteria below, then the subject is discontinued from the study and will not be replaced. 1. Limbal exposure in any gaze 2. Edge lift 3. Insufficient and/or excessive movement in all three movement categories	

Visit 2: Treatment 1 Follow-Up			
Step	Procedure	Details	
2.10.	Surface Deposits	Record any front and back surface lens deposits.	
2.11.	Lens Removal & Storage	Both lenses will be removed and stored wet in a labeled container with Opti-Free® PureMoist®. The lenses can be stored refrigerated or frozen prior to shipment back to the Sponsor. Lenses will be stored at JJVC for 45 days after LSLV for laboratory testing (Section 7.4).	
2.12.	Slit Lamp Findings	
Slit Lamp Classification Scale [REDACTED] will be used to grade the findings. Record only whole numbers. Limbal and Bulbar Conjunctival Hyperemia findings [REDACTED] [REDACTED] and Corneal Staining Assessment [REDACTED] [REDACTED] will be emphasized using a more detailed scale.
 
Note: Findings must be grade 2 or less as graded on the FDA scale [REDACTED] to continue onto Trial Period 2. If the subject is not eligible, they must be followed as an adverse event. Once resolved, the subject is terminated from the study. Adverse events must be reported to the JJVC monitors immediately.
	[REDACTED] [REDACTED] [REDACTED]

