4. STUDY ENDPOINTS

4.1. Primary Endpoints

Primary Efficacy Endpoints:

CLUE Overall Comfort

Overall comfort scores will be assessed using the Contact Lens User Experience (CLUE™)¹ questionnaire at the two-week follow-up. CLUE is a validated patient-reported outcomes questionnaire to assess patient-experience attributes of soft contact lenses (comfort, vision, handling, and packaging) in a contact-lens wearing population in the US, ages 18-65. Derived CLUE scores, using Item Response Theory (IRT), follow a normal distribution with a population average score of 60 (SD 20), where higher scores indicate a more favorable/positive response. A 5 point increase in an average CLUE score translates into 10% shift in the distribution of scores for a population of soft contact lens wearers¹. The handling scores will be generated using the flexMIRT software version 3 or higher (Chapel Hill, NC).

Distance Monocular Contact Lens Visual Acuity

Distance monocular contact lens visual performance (logMAR) is assessed for each subject eye at the two-week follow-up evaluation using EDTRS charts under two lighting conditions, (1) Bright illumination low contrast and (2) Dim Illumination High Contrast.

Vision Satisfaction in Bright Lighting

Vision satisfaction in bright lighting will be assessed using the individual item [REDACTED] “I was satisfied with the quality of my vision in bright lighting” from the CLUE™ questionnaire.

This item uses the response scale, 1: Strongly Disagree, 2: Disagree, 3: Neither Agree nor Disagree, 4: Agree and 5: Strongly Agree.

Primary Safety Endpoints:

Slit Lamp Findings (Grade 3 or Higher)

Slit Lamp Findings will be assessed using the FDA Grading scale ranging from 0 to 4, where Grade 0 represents the absence of findings and 1 to 4 representing successively worse findings (i.e. Grade 1=trace, Grade 2= mild, Grade 3=moderate and Grade 4= severe). The assessment will include conjunctival injection, corneal edema, corneal neovascularization, corneal staining, tarsal abnormalities or any other complication. SLF assessments will be conducted for each subject eye at all scheduled study visits(Fitting [Visit 1] and 2-Week Follow-up [Visit 2]). The percentage of eyes with Grade 3 or higher slit lamp findings will be analyzed; eyes with multiple events will be counted only once.

Fit Acceptance Rate

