10.2. Protocol Deviations

Any protocol deviation that could impact the primary endpoints will result in the subject being excluded from the Per-Protocol analysis population. No analysis on protocol deviations will be performed. All reported protocol deviations will be listed.

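### The SAP states two populations for the primary lens-fit and slit lamp tests; under Per-Protocol the fit test can hardly fail and the Grade 3+ odds ratio is practically not estimable

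*SAP*

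**What the plan says.** SAP 4.1 lists slit lamp findings and fit acceptance under "Primary Safety Endpoints", and SAP 11.1 tests them as primary safety analyses within the primary analysis. Two sentences then set the population:

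- SAP 6.3: "Safety analyses will be based on the safety population".
- SAP 6.4: "Per Protocol Analysis set will be the primary analysis population". The set is defined next: "It will include all subjects who have successfully completed all visits and did not substantially deviate from the protocol".

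SAP 11.1 names no population for any test. Protocol 14.3 defines the sets without assigning them. SAP 10.2 refers to the primary endpoints without separating efficacy from safety: "Any protocol deviation that could impact the primary endpoints will result in the subject being excluded from the Per-Protocol analysis population".

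The discontinuation rules are in Protocol 7.2:

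- **Fit** (steps 1.22, 2.9, 2.21, 3.10, 3.22). If the fit is unacceptable, "then the subject is discontinued from the study and will not be replaced".
- **Slit lamp at Visits 2 and 3** (steps 2.12, 3.13). Findings must be Grade 2 or less to continue. "If the subject is not eligible, they must be followed as an adverse event. Once resolved, the subject is terminated from the study".
- **Slit lamp at Visit 4** (step 4.12). A higher grade is followed as an adverse event, with no termination.
- **Unscheduled visits** (step U.5). There is no written termination rule for a Grade 3+ finding.

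**The concern.** In most trials a completer population selects on something related to the outcome. Here the endpoint event itself triggers the exclusion. A subject whose Test lens fits unacceptably at Visit 1, 2 or 3 fails the endpoint and, by the same event, leaves the PP set. The same holds for a Grade 3+ finding at Visit 2 or 3.

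All primary hypotheses must be met (SAP 5.1). If the population is settled after the data are seen, the choice can settle the fit conclusion. It can also determine whether the Grade 3+ comparison can be made, or whether the SAP's fallback to Grade 2+ is used instead.

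**Working it through.** The plan gives no figure for the effect of the population. The sizes in SAP Table 11 (65 for fit, 50 for slit lamp) are counts of completers and do not address it.

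**Inputs.** 120 enrolled, 60 per sequence, or 114 randomized, 57 per sequence (SAP Table 2). Correlations of 0.80 within a period and 0.50 across periods (SAP 8.4). Fit succeeds if the lower 95% bound exceeds 0.90; slit lamp succeeds if the upper 95% bound of the odds ratio is below 2 (SAP 11.1). Assumption: a Visit 4 failure stays in PP.

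**1. Which events can reach PP**

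| | Test-lens fit assessments | Can a failure be in PP? |
|---|---|---|
| Test/Control/Control | Visit 1 fitting, Visit 2 follow-up | no, no |
| Control/Test/Test | Visit 2 fitting, Visit 3 follow-up, Visit 3 fitting, Visit 4 follow-up | no, no, no, yes |

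One of six can. For Grade 3+ findings, one of three scheduled follow-ups per lens can (Visit 4), for Test and Control alike. If the visit list in SAP 4.1 (Visits 1 and 2 only) is taken literally, PP contains no fit failure and no Grade 3+ finding.

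**2. Lens fit: chance of declaring success (simulation)**

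| True acceptance per assessment | Safety | PP |
|---|---|---|
| 90% (null) | about 9-94% | about 100% |
| 85% | about 0-32% | about 100% |
| 80% | about 2% or less | about 95-100% |

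The low end of the Safety range comes from one fit outcome per eye and period. The high end comes from separate fitting and follow-up assessments in each period.

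For scale, with one record per eye and an exact interval, the Safety test first fails at 6 of 120 subjects if eyes are fully correlated (lower bound for 114/120 is 0.894; for 115/120 it is 0.905). If eyes are independent it first fails at 15 of 240 eyes (lower bound for 225/240 is 0.899). That is a failure rate of about 5-6%.

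**3. Why Safety is still biased.** Take the extreme case in which 10% of subjects always fail and 90% never do. With 60 per sequence, 6 + 6 = 12 subjects fail at their first Test fitting and contribute one assessment each. The other 54 + 54 contribute 54 × 2 + 54 × 4 = 324. Safety shows 324 / (324 + 12) = 96.4% for a true 90%; PP shows 324 / 324 = 100%.

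**4. Slit lamp: number of events.** With 114 subjects and a 5% rate per eye-period on both lenses, simulation gives about 9.5 Test eye-events in Safety and 1.5 in PP. The loss is (9.5 − 1.5) / 9.5 = 84%.

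**5. Slit lamp: estimability.** Let d1, d2, d3 be the difference in log odds between Test/Control/Control and Control/Test/Test in each period. With the SAP's coding (Test = 1, Test/Control/Control = 1, carryover = previous lens, 0 in period 1):

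- d1 = β1 + β5
- d2 = −β1 + β5 + β6
- d3 = −β1 + β5 − β6

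Hence β1 = (2·d1 − d2 − d3) / 4. In PP there are no Grade 3+ findings at the scheduled follow-ups of periods 1 and 2, so d1 and d2 have no finite estimate. In period 3, Lens = Carry = 1 − Sequence, so d3 alone cannot isolate β1.

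A posterior run of the fixed effects, without random effects and reading the N(0, 10000) prior as a variance, gave these 95% intervals for β1:

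- events in period 3 only, 3 per sequence: about −121 to +97
- 3 events in every period and sequence: −1.10 to +1.09

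The bound to beat is log 2 = 0.69.

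**6. Slit lamp: chance of declaring non-inferiority.** Simulation with lens as the only term and a true odds ratio of 1:

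| Grade 3+ rate | Safety | PP |
|---|---|---|
| 5% | 18-21% | 1% |
| 10% | 34-36% | 4% |

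At a true odds ratio of 2, both populations declare non-inferiority in under 1% of trials.

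**The case against.** **SAP 6.3 is the specific rule.** Both endpoints carry the safety label, so a careful analyst may well use the Safety set, and SAP 10.2 only defines deviation exclusions. This is a reasonable reading. But the SAP does not say that 6.3 overrides 6.4, and 6.4 makes no exception.

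**History suggests few failures.** There were no Grade 3+ findings, and no unacceptable Test fit (Protocol Table 7) or one (SAP Table 8). At such rates fit passes in either population, and at the planned 95% Safety passes in most trials. This stands: the choice matters only if the lens fits worse than expected. Protocol section 1, however, describes lenses from a new manufacturing line being evaluated clinically for the first time, so a departure from history is what the test should be able to detect.

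**Grade 2+ fallback.** If Grade 3+ findings are too few, Grade 2+ is tested (SAP 11.1). Grade 2 does not end participation, so the population matters much less there. This also stands, and the fallback is likely: SAP Table 9 shows 108 Grade 2 findings on Test and none at Grade 3+. But PP removes Grade 3+ events and can itself trigger the switch.

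**Stronger readings to avoid.** A reader might infer that PP gives both safety tests an easy pass. For slit lamp it does the opposite, because events are lost on both lenses and the interval widens. A reader might also infer that PP removes every early Grade 3+ finding. No termination rule is written for unscheduled visits, although SAP 8.2 leaves those visits out of the statistical analysis.

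**Conclusion.** The conflict is real, and SAP 6.3, 6.4 and 11.1 do not resolve it. For lens fit the consequence is serious: under PP the test passes in about 95-100% of simulated trials at true rates from 80% to 95%, so it cannot detect a poorly fitting lens. This follows mainly from the visit structure and held in every model tried. The Safety pass rates depend heavily on how fit is modelled and should be read only as showing that the test can then fail.

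For slit lamp, PP leaves only Visit 4 events from the scheduled follow-ups. The planned Grade 3+ odds ratio becomes practically non-estimable and non-inferiority harder to show.

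The choice therefore does not decide both primary safety results in all circumstances. It can decide the fit result if failures reach roughly 5-6%, and it can determine whether the Grade 3+ test is usable. These conclusions assume the SAP's stated correlations and that Visit 4 failures remain in PP.

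**What to change.** Before database lock:

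- **SAP 6.4:** state that PP is the primary population for the efficacy endpoints only.
- **SAP 10.2:** limit the reference to the primary efficacy endpoints.
- **SAP 11.1:** state that the primary lens-fit and slit lamp tests use the Safety population, with every eye record on each lens up to and including the visit at which the subject is discontinued, and PP as a sensitivity analysis.
- **SAP 11.1:** state that Safety reduces the bias without removing it, because follow-up stops at the first failure and subjects who fail early contribute fewer records.

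This changes wording only and needs no new data. The cost is that the fit result may be less favourable than under PP. The slit lamp comparison keeps more events.
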